3.2 Principal objective

The primary objective of TRIHEP 3 is to evaluate the efficacy of triheptanoin in slowing atrophy in the caudate of early affected HD patients as measured with volumetric magnetic resonance imaging.

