3.4 Primary endpoint

The primary efficacy endpoint is the change from baseline to 6 months in caudate atrophy as measured by caudate boundary shift integral (cBSI).

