4.2 Measures to limit bias

Double-blind, randomized design.

SAP001V04/TRIHEP3

Last date of modification: 09/01/2019

Biostatistician: [name]/[name]

5 Number of necessary subjects

The rate of progression of caudate atrophy is linear in HD patients at an early-disease stage (Tabrizi SJ, Scahill RI, Owen G, et al. Predictors of phenotypic progression and disease onset in premanifest and early-stage Huntington's disease in the TRACK-HD study: analysis of 36-month observational data. *Lancet Neurol.* 2013;12(7):637-649). We hypothesized that, in patients under placebo, the progression of caudate atrophy over 6 months would be reduced by 42%. Based on such hypothesis and data from the TRACK-HD study, fifty patients under placebo and fifty patients treated with triheptanoin would be required to achieve 80% power at the one-sided 0.025 alpha level. Therefore, a total of 100 patients was required.

6 Study population

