6.3 Population to analyze

Intent-to-treat (ITT) Population

The main efficacy analysis will be based on all data in the intention-to-treat population defined as all randomized patients who have signed an informed consent form. In case of consent withdrawal, only data collected before withdrawal will be used. All patients will be analyzed on the basis of their randomized group of treatment.

Per-Protocol (PP) Analysis Set

In addition, an explanatory analysis (PP) of all patients randomized and treated without major protocol violations/deviations will be carried out. Pre-defined major protocol violations/deviations are:

1. Missing data for the primary efficacy endpoints
2. Premature discontinuation of treatment, whatever the reason.
3. Unjustified change in treatment during follow-up
4. Inclusion in another clinical study

7 Variables measured and kept for analysis

All variables of the eCRF and those in additional files reporting data from MRI are kept for analysis. Regarding these latter following variables will be used:

- Index of brain energy restoration:

The delta of activation-recovery from the Pi/PCr ratio measured by ³¹phosphorous MRS will be taken as the index of brain energy restoration.

- Caudate atrophy:

This will be the caudate volume loss (proportion of baseline volume) as measured by the caudate boundary shift integral (cBSI).

- Diffusion tensor metrics:

Fractional anisotropy (FA), radial diffusivity (RD), mean diffusivity (MD).

- Fiber tracking metrics:

Fiber density (FD), fiber cross-section (FC) and a combination of both - fiber density and cross-section (FDC).

SAP001V04/TRIHEP3

Last date of modification: 09/01/2019

Biostatistician: [name]/[name]

Diffusion tensor metrics and fiber tracking metrics will be analyzed in the following areas from the JHU-atlas:

- Middle cerebellar peduncle
- Pontine crossing tract
- Genu of corpus callosum
- Body of corpus callosum
- Splenium of corpus callosum
- Fornix
- Corticospinal tract
- Medial lemniscus
- Inferior cerebellar peduncle
- Superior cerebellar peduncle
- Cerebral peduncle
- Anterior limb of internal capsule
- Posterior limb of internal capsule
- Retrolenticular part of internal capsule
- Anterior corona radiata
- Superior corona radiata
- Posterior corona radiata
- Posterior thalamic radiation
- Sagittal stratum
- External capsule
- Cingulum (cingulate gyrus)
- Cingulum (hippocampus)
- Fornix (cres) / Stria terminalis
- Superior longitudinal fasciculus

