The difference between the two groups regarding change from baseline in caudate atrophy at M6 will be analyzed using an ANOVA (SAS PROC MIXED) with Kenward-Roger's adjusted degrees of freedom. Adjusted analysis will be performed using ANCOVA with age, gender and BMI as covariates. Prior to performing statistical tests, the assumptions of normality and

SAP001V04/TRIHEP3

Last date of modification: 09/01/2019

Biostatistician: [name]/[name]

homogeneity of variances of residuals were tested using Shapiro-Wilk test and Levene's test respectively. If the data meet the normality assumption and do not meet homogeneity assumption, proc mixed allows to estimate separately the variance-covariance matrices in repeated statement using group option and thereby overcome the issue of heterogeneity of variance. If the data do not meet the normality or homogeneity assumptions of the parametric tests and are highly skewed, then a rank analysis was used.

Secondary criteria

- The difference between the two groups regarding change from baseline in index of brain energy restoration at M3, M6 and M12 (defined as delta of activation-recovery from the Pi/PCr ratio measured by ³¹phosphorous MRS) will be analyzed using ANCOVA with baseline value as covariate. Adjusted analysis will be performed using ANCOVA with baseline value, age, gender and BMI as covariates
- The difference between the two groups regarding change from baseline in caudate atrophy at 1 year will be analyzed using ANOVA. Adjusted analysis will be performed using ANCOVA with age, gender and BMI as covariates.
- Diffusion tensor metrics and fiber tracking metrics will be analyzed using ANCOVA.
- Clinical scores will be analyzed using ANCOVA with baseline value as covariates. Adjusted analyses will be performed using an ANCOVA with baseline value, age, gender and BMI as covariates.
- Long-term compliance will be confirmed by regular biochemical testing from blood and urine samples – especially the levels of plasma propionylcarnitine and urinary 3-hydroxypropionic, 2-methylcitric, propionylglycine, tiglylglycine and/or methylmalonic acid – as well as by oil container accounting at study visits. The number of patients with detectable levels of triheptanoin metabolites will be reported.

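### The primary cBSI model ignores the actual baseline-to-M6 scan interval; the cost is small unless mean intervals differ between arms, and one covariate would cover that case (minor)

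*SAP*

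**What the plan says.** - **Objective (section 3.2):** to "evaluate the efficacy of triheptanoin in slowing atrophy in the caudate of early affected HD patients".
- **Endpoint (section 3.4):** "The primary efficacy endpoint is the change from baseline to 6 months in caudate atrophy as measured by caudate boundary shift integral (cBSI").
- **Analysed variable (section 7):** "This will be the caudate volume loss (proportion of baseline volume) as measured by the caudate boundary shift integral (cBSI"). It is not expressed per unit of time.
- **Primary model (Primary endpoints, in section 9):** "The difference between the two groups regarding change from baseline in caudate atrophy at M6 will be analyzed using an ANOVA (SAS PROC MIXED"). For the adjusted version, "Adjusted analysis will be performed using ANCOVA with age, gender and BMI as covariates". Scan interval is in neither model.
- **Time course (section 5):** "The rate of progression of caudate atrophy is linear in HD patients at an early-disease stage".
- **Off-schedule scans:** the intention-to-treat analysis in section 6.3 uses all data, and its four listed major deviations do not include a scan made early or late. A visit window may be in the protocol, which is not at hand, so its absence from the SAP is not the point here.

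**The concern.** If loss accrues linearly, the expected cBSI loss is proportional to the time between the two scans. With the interval left out, a patient scanned early looks like a slow progressor and a patient scanned late like a fast one. If one arm were scanned later on average, for instance because visits slipped for tolerability reasons, that delay would be part of the estimated treatment difference. It would favour triheptanoin if the control arm were scanned later and mask an effect if the triheptanoin arm were.

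A related case is a control patient whose M6 scan falls after the start of the open-label phase (section 4.1). That scan would include some active exposure and still count as placebo.

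Deriving the primary variable and choosing its covariates are SAP matters. A protocol window would limit the variation but would not adjust for what remains inside it.

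**Working it through.** **The plan's own figure.** Section 5 gives 50 per arm, a 42% reduction, 80% power and one-sided 0.025, but no mean loss and no SD. The sample size therefore cannot be reproduced, only solved backwards. I read the 42% as the effect of triheptanoin relative to placebo.

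- Normal approximation: d = (1.960 + 0.842) × √(2/50) = 0.560.
- Noncentral t: d = 0.566, used below.
- Mean placebo loss over 6 months = 0.566/0.42 = 1.35 SD, so SD = 0.742 of mean placebo loss.

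**Assumptions not in the SAP:** a 26-week nominal interval, uniform timing deviations, equal SD in both arms, and the sizes of the timing differences.

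**Case 1: mean interval differs between arms.** One week is 1/26 = 3.8% of the 6-month loss.

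- Shift at the placebo rate: 1.35/26 = 0.052 SD. As a share of the planned effect: (1/26)/0.42 = 9.2%.
- Shift at the arms' average rate, (1 + 0.58)/2 = 0.79 of placebo: 0.79 × 9.2% = 7.2%.
- If the planned effect is real and only the triheptanoin arm is displaced: 0.58 × 9.2% = 5.3%.

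These shares depend only on the 42% and the 26 weeks. The back-solved SD is needed for the type I error, shown here with no true effect:

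| Assumed mean difference | Share of planned effect (placebo rate) | Two-sided type I error |
|---|---|---|
| 1 week | 9% | 0.058 |
| 2 weeks | 18% | 0.081 |
| 4 weeks | 37% | 0.177 |

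**Case 2: timing unrelated to arm.** For deviations of ±h weeks, the relative SD of the interval is s = h/(26√3). In units of mean placebo loss, the variance of unscaled loss is

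- 0.742² + s²(1 + 0.58²)/2 if the spread between patients is all measurement error;
- 0.742²(1 + s²) + s²(1 + 0.58²)/2 if it is all true variation in rate.

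| h | s | Variance factor | Power, unscaled |
|---|---|---|---|
| 2 | 0.044 | 1.002 to 1.004 | 79.9 to 79.8% |
| 4 | 0.089 | 1.010 to 1.017 | 79.6 to 79.3% |
| 8 | 0.178 | 1.038 to 1.070 | 78.5 to 77.3% |

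Against 80.0%, the loss is 0.1 to 2.7 points. Simulated two-sided type I error over 100,000 trials was 0.050 at both ±4 and ±8 weeks.

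**Covariate or division?** I simulated power under the planned effect (40,000 trials per setting, Monte Carlo SE about 0.2 points):

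| Source of spread | h | Unscaled | Divided by interval | Interval as covariate |
|---|---|---|---|---|
| All true rate | 2 | 79.9% | 80.1% | 79.5% |
| All true rate | 8 | 77.7% | 80.3% | 78.7% |
| All measurement error | 2 | 79.8% | 79.7% | 79.5% |
| All measurement error | 8 | 78.4% | 76.0% | 79.4% |

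Division helps when the spread is true rate variation and loses power when it is measurement error. The covariate stays within about 0.4 points of the unscaled analysis at ±2 weeks and gains about 1 point at ±8 weeks in both settings.

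**The case against.** The strongest reply is that the plan is coherent as written. Sections 3.4, 5, 7 and 9 all concern loss over a fixed six months, and slowing can properly be judged as less loss at a fixed time. The linearity sentence supports the sample size and does not commit the plan to a rate endpoint. Windows and scan scheduling are usual protocol content. The trial is randomised and double-blind to M6, and section 9 calls it mainly exploratory.

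Most of this stands. There is no contradiction between the sections. A reader might infer that scan-timing differences are counted as drug effect; the SAP does not support that. Without a systematic cause, timing variation is random error and is already in the ANOVA standard error. With ±4 weeks of spread, the chance difference in mean interval has an SE of (4/√3) × √(2/50) = 0.46 weeks, so a 2-week difference would be more than 4 SE. Nor does one very late patient matter much: a scan 13 weeks late moves that patient by 1.35/2 = 0.67 SD, but the arm mean by only 0.67/50 = 0.013 SD.

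What the reply does not remove is that the SAP fixes both the variable and the covariates without time, and does not specifically call for the interval by arm. A systematic difference, if it occurred, could pass unseen.

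**Conclusion.** The point holds as a minor improvement to the primary analysis. Timing unrelated to arm costs about 0.1 to 2.7 points of power for assumed deviations of ±2 to ±8 weeks and does not inflate the type I error. A difference between arms in mean interval would bias the contrast by about 7 to 9% of the planned effect per week, in either direction.

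The stronger inference, that the primary comparison is biased as planned, would need evidence that mean intervals differ by arm, and the SAP contains none. Nor does it show that any control M6 scan falls after the switch.

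The figures rest on the back-calculation from 50 per arm, 80% power and 42%, a 26-week interval, and linear loss. Section 5 states linearity for early HD patients in general, not specifically under triheptanoin.

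**What to change.** Amend sections 7 and 9 before unblinding:

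1. Add the actual baseline-to-M6 scan interval, in days and centred at 6 months, as a covariate in the primary cBSI model and in its adjusted version. Where the M6 scan is missing, impute loss at the nominal interval (centred covariate zero).
2. Give two sensitivity analyses: loss rescaled linearly to 6 months, and unscaled loss without the covariate.
3. Tabulate the scan interval by arm.
4. For M6 scans made after the open-label switch, run a sensitivity analysis that applies one timing cut-off to both arms. Setting only control-arm scans to missing would be an arm-specific exclusion after randomisation, at odds with the all-data intention-to-treat analysis in section 6.3.
5. Do not rescale the 1-year endpoint linearly. Controls change treatment at six months, so a single slope over 12 months is doubtful for them.

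**Cost:** SAP wording, one variable derived from the scan dates, one table, one degree of freedom, and reliance on the linearity already stated. The interval is observed after randomisation, so if delays were related to both treatment and progression, the covariate would not fully correct for them. The table by arm and the sensitivity analyses would help show whether that matters.

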3.1 Hypothesis

Our proof-of-concept study strongly suggests that triheptanoin is able to improve the brain metabolic profile of HD patients at an early stage of the disease. It is very unlikely that these changes in brain energy metabolism are observed by chance as we have previously validated that the Pi/PCr changes in HD patients are stable over time, including over a one-month interval. Of note, the correction of the Pi/PCr response during brain activation was particularly notable when compliance to triheptanoin was ensured. We also observed an interesting trend of improved motor functions in HD patients after one month of anaplerotic therapy although these findings have to be interpreted with caution due to a possible placebo effect in this open-label study.

Thanks to neuroimaging biomarkers already validated in HD and the newly identified metabolic brain biomarkers using ³¹phosphorous magnetic resonance spectroscopy (MRS), we can test for a reduction in neurodegeneration among HD patients resulting from an improvement in brain energy profiles with triheptanoin.

SAP001V04/TRIHEP3

Last date of modification: 09/01/2019

Biostatistician: [name]/[name]

In our follow-up study, TRIHEP 3, we plan to include 100 early affected HD patients ($5 \leq \text{UHDRS} \leq 40$) in a randomized, double-blind, controlled study in 2 centers (France and the Netherlands). Patients will receive either triheptanoin at 1g/kg of body weight per day ($n = 50$), or a control oil ($n = 50$) for 6 months followed by an open label phase using triheptanoin for another 6 months. Efficacy of triheptanoin will be evaluated by measurements of caudate volume using volumetric magnetic resonance imaging and brain energy metabolism as evaluated by the ratio of inorganic phosphate/phosphocreatine, during visual stimulation, using ^{31}P -MRS. Clinical improvement will be evaluated by UHDRS, TFC, and PBA-S score as well as performance on the neurocognitive battery; patient quality of life will be evaluated with the SF-36 questionnaire before and after treatment; biological tolerance and compliance will be evaluated by routine biochemical blood tests, plasma and urine measurements of triheptanoin oil derivatives and patient report.

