- Superior fronto-occipital fasciculus
- Uncinate fasciculus
- Tapetum

8 Missing data

For the main criterion a multiple imputation technic will be used in case of missing data (SAS PROC MI). No imputation will be used for secondary criteria.

SAP001V04/TRIHEP3

Last date of modification: 09/01/2019

Biostatistician: [name]/[name]

9 Statistical analysis

Tabulated descriptive statistics by treatment will be provided for all parameters recorded in the eCRF.

Analysis of Continuous Data:

Continuous variables will be summarized using number of observations, mean, standard deviation, minimum, maximum, 25%, 50%, 75% quantiles and the two-sided 95% confidence intervals. Means, medians, minimum, maximum and standard deviations will be presented to one further decimal place. In addition, 95% confidence interval of difference between groups will be reported. Exact confidence intervals will be used if required.

Analysis of Categorical Data:

There will be counting of the absolute and relative frequencies (percentages) for categorical variables. Percentages will be rounded to one decimal place and there may be occasions where the total of the percentages does not equal 100% exactly.

General considerations regarding alpha value:

The nature of this study is mainly exploratory. We identified a main criterion for which a 5% two-sided alpha value has been chosen for statistical inference. As regards to the secondary criteria, we did not adjust alpha value for multiplicity since all the statistical inference regarding these numerous criteria should be considered as exploratory.

General considerations regarding parametric or non-parametric procedures:

All variables will be checked for their gaussian distributions by Shapiro-Wilk 's test. In case of non-normality, a normalizing transformation will be used. If this procedure failed a rank analysis will be used.

Demographic and other baseline characteristics data will be summarized descriptively as described above and will be summarized using Consort standard tabulations and listings will be generated.

Disposition of patients, patient status and patients excluded from ITT, PP populations will be summarized by treatment group. Descriptive statistics for primary reason for patient's withdrawal will be also presented by treatment group as well as a list of these patients sorted by treatment group.

Primary endpoints:

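### Minor, precision only: the M6 and 1-year cBSI comparisons leave baseline caudate volume, CAG length and centre out of both planned models; one pre-named ANCOVA would be an inexpensive improvement of unproven size

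*SAP*

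**What the plan says.** SAP Section 9, Primary endpoints, states that the M6 comparison of cBSI change "will be analyzed using an ANOVA (SAS PROC MIXED") with Kenward-Roger degrees of freedom. It names no covariate. It then adds: "Adjusted analysis will be performed using ANCOVA with age, gender and BMI as covariates". It does not say in words which of the two is primary; the ANOVA is the natural reading. Under Secondary criteria, "change from baseline in caudate atrophy at 1 year will be analyzed using ANOVA", with the same age/gender/BMI version beside it.

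The three variables in neither model appear elsewhere in the SAP:

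- **Centre:** Section 3.1 describes a "controlled study in 2 centers (France and the Netherlands").
- **CAG length:** Section 6.1 uses it as an entry criterion, at least 39 repeats.
- **Baseline caudate volume:** Section 7 defines the endpoint through it: "This will be the caudate volume loss (proportion of baseline volume").

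Section 7 also says: "All variables of the eCRF and those in additional files reporting data from MRI are kept for analysis". Section 5 sizes the trial: fifty per arm "would be required to achieve 80% power at the one-sided 0.025 alpha level". Section 9 remarks of the whole trial: "The nature of this study is mainly exploratory".

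**The concern.** In a randomised comparison of a continuous outcome, variance that a baseline variable explains stays in the error term unless the variable is in the model. The M6 cBSI test is the one test for which the SAP reserves its 5% two-sided alpha, and it was sized at 80% power with 100 patients. Its main analysis uses no baseline information beyond the scaling built into the endpoint. The adjusted version uses three general variables, and the SAP gives no reason for preferring them to a disease-related or design variable. If the omitted variables predict 6-month cBSI loss, some power is given up. If they do not, nothing is lost. Bias and type I error are not at stake.

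**Working it through.** **Inputs from the SAP.** 50 per arm, 80% power, one-sided 0.025 (Section 5), which equals the two-sided 5% in Section 9. The assumed effect is a 42% reduction in 6-month atrophy.

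**The plan's own figure.** The sample size cannot be reproduced forward, because the SAP gives no mean or SD for 6-month cBSI change. It can be inverted. A two-sample t test with 98 degrees of freedom has 80% power at 50 per arm when the standardised effect is d = 0.566 (noncentral t). With a 42% reduction this implies SD/mean = 0.42 / 0.566 = 0.74 for placebo atrophy. All power below is anchored to this d.

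**Assumed.** R², the share of cBSI variance that the covariates explain; and all 100 patients analysed.

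**Formula.** With k covariates and N = 100:

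- variance inflation from chance imbalance: VIF = (N - 3) / (N - k - 3)
- effective effect: d / √((1 - R²) × VIF)
- degrees of freedom: 98 - k

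Example, k = 4 and R² = 0.10: VIF = 97/93 = 1.043; effective d = 0.566 / √(0.90 × 1.043) = 0.584; noncentrality = 0.584 × √(50/2) = 2.92 on 94 degrees of freedom; power 82.4%.

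**1. Against the unadjusted ANOVA (80%)**

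| R² | k = 3 | k = 4 | k = 6 |
|---|---|---|---|
| 0 | 78.7% | 78.3% | 77.4% |
| 0.05 | 80.7% | 80.3% | 79.5% |
| 0.10 | 82.8% | 82.4% | 81.6% |
| 0.20 | 86.9% | 86.6% | 85.8% |
| Break-even R² | 0.032 | 0.042 | 0.063 |

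k = 3 is the size of the SAP's age/gender/BMI set. k = 4 is baseline volume, age, centre and CAG length, and its R² includes the part due to age. k = 6 adds the three omitted variables to the SAP's set. Each covariate that explains nothing costs about 0.4 points; four cost 80.0 - 78.3 = 1.7 points and six cost 80.0 - 77.4 = 2.6.

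**2. Against the SAP's age/gender/BMI model, taken at R² 0.10 (82.8%)**

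| R² of four-covariate model minus 0.10 | Change in power (points) |
|---|---|
| -0.05 | -2.5 |
| -0.02 | -1.2 |
| 0 | -0.4 |
| +0.02 | +0.4 |
| +0.05 | +1.7 |
| +0.10 | +3.8 |

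Break-even is an R² difference of about +0.01. The negative rows belong in the range because the four-covariate set drops gender and BMI and could explain less.

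**Check.** In a simulation of 20,000 trials with six independent normal covariates and total R² 0.10, split equally between two sets of three, power was 80.3% unadjusted, 81.0% with either set of three and 81.6% with all six. The formula gives 80.0%, 80.7% and 81.6%. A simpler calculation that ignores VIF gives 84.0% at R² 0.10 and almost no cost at R² 0; the figures above are the more cautious.

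**The case against.** The strongest reply is that this is a preference, not a defect. The SAP pre-specifies a valid unadjusted comparison and a pre-specified adjusted one. Nothing in it shows that centre, CAG length or baseline volume predicts proportional caudate loss over 6 months, and a grid of assumed R² values shows only what would follow if they did. That stands. It limits the point to a suggestion.

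Three further replies also stand:

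- **Baseline volume is partly handled already.** The endpoint is a within-patient loss scaled to baseline volume, so the covariate may add little.
- **Availability is partly inferred.** Section 7 keeps all eCRF and MRI variables, but its list of MRI variables to be used gives the proportional loss and no absolute baseline volume. A baseline volume is implied by the definition. Whether the eCRF holds the CAG number, beyond the entry threshold, is not shown.
- **The swap can lose.** Gender and BMI might prove the more prognostic, as the negative rows above show.

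Some stronger readings are tempting, and the SAP does not support them. A reader might infer a contradiction because the energy index and clinical scores are adjusted for their baseline value and cBSI is not; the proportional definition of cBSI is a sufficient reason for the difference. A reader might infer that leaving out centre conflicts with the randomisation; the SAP does not say that randomisation was stratified by centre, so the case for centre rests on prognostic value alone.

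**Conclusion.** The point holds as a minor, optional gain in precision. The M6 and 1-year cBSI comparisons rest on an ANOVA without covariates, and the single adjusted version omits baseline caudate volume, CAG length and centre. It should not be read as saying that the primary analysis is biased, that its type I error is wrong or that 50 per arm is too few; none of these follows.

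The size depends wholly on an unknown R². The change helps against the ANOVA only if the four covariates explain more than about 4% of cBSI variance, and against the age/gender/BMI model only if they explain about 1 percentage point more than it does. At R² 0.10 to 0.20 the gain over the ANOVA is 2.4 to 6.6 points of power. These figures rest on the 80% anchor at 50 per arm, a linear model and complete data. The SAP's own description of the study as mainly exploratory keeps the weight low.

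**What to change.** Before unblinding, name one ANCOVA as the primary analysis of M6 cBSI: treatment plus baseline caudate volume, age, centre and, if the eCRF records the number, CAG length. Use the same set for the 1-year cBSI model. Keep the ANOVA and the age/gender/BMI model as sensitivity analyses, so that no planned result is lost. Gender and BMI stay out of the primary model only to limit its terms.

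The sponsor should first confirm the set on blinded or external data. If those data favour gender or BMI, or show an R² below break-even, the set should change or the ANOVA should stay. Whatever is decided, the SAP should say in words which model is primary.

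The cost is SAP wording and four of 98 degrees of freedom. If the covariates explain nothing, power falls by about 0.4 points for each, or 1.7 points for four, against the ANOVA. A small loss against the age/gender/BMI model is also possible. No new data collection is expected, provided that baseline volume and the CAG number are on file.

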Statistical Analysis Plan

Ref: SAP001V04

TRIHEP 3

A comparative phase 2 study assessing the efficacy of triheptanoin, an anaplerotic therapy in Huntington’s Disease

Sponsor Inserm n°: C14-62

Coordinating Investigator: [name]
Département de Génétique
ICM UPMC, Inserm UMR_S1127/CNRS
UMR 7225

[name] Biostatistician	[name] Reviser position:	[name] Approver’s position:
Date : 09/ 01/2019 (DD/MM/YYYY)	Date : 09/01/2019 (DD/MM/YYYY)	Date : 09/01/2019 (DD/MM/YYYY)
Signature :	Signature	Signature :

ABBREVIATIONS

31P-MRS	31-Phosphorus Magnetic Resonance Spectroscopy (³¹ P-MRS)
ANOVA	Analyse of Variance
ANCOVA	Analyse of Covariance
CAG	Cytosine-Adenine-Guanine Cr = Creatine
HD	Huntington's disease
HTT	Huntingtin
MRI	Magnetic Resonance Imaging
PBA-S	Problem Behavior Assessment Short version
PCr	Phosphocreatine
Pi	inorganic Phosphate
SAP	Statistical Analysis Plan
SDMT	Symbol Digit Modality Test
SF-36	Short Form 36
TFC	Total Functional Capacity
TMT	Trail Making Test
UHDRS-TMS	Unified Huntington's Disease Rating Scale Total Motor Score

SAP001V04/TRIHEP3

Last date of modification: 09/01/2019

Biostatistician: [name]/[name]

SAP001V04/TRIHEP3	Date of modification: 09/01/2019
	Biostatistician: [name]/[name]

POP_TE116	Effective on: 09/01/2019	Version: 04
-----------	--------------------------	-------------

1 History of modifications

Version	Author	Modification description	Date
V01	[name]	Draft SAP creation	08/10/2018
V02	[name]	Revision	02/01/2019
V03	[name]	Edits	06/01/2019
V04	[name]	Finalization	09/01/2019

SAP001V04/TRIHEP3

Last date of modification: 09/01/2019

Biostatistician: [name]/[name]

2 Introduction

This Statistical Analysis Plan (SAP) is prepared by the URC Lariboisiere for a 2 centers, randomized, double-blind, placebo-controlled study (the TRIHEP3 Trial) to evaluate the benefit of triheptanoin in early affected HD patients compared to placebo, the study entitled: A comparative phase 2 study assessing the efficacy of triheptanoin, an anaplerotic therapy in Huntington's Disease (Project Code: C14-62, ClinicalTrials.gov Identifier: NCT02453061, EUDRACT No.: 2014-005112-4).

The primary objective of this clinical trial is to assess the efficacy of triheptanoin compared to placebo in decreasing of the caudate volume using volumetric magnetic resonance imaging.

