3.3 Secondary objective(s)

The secondary objectives are:

- To assess the efficacy of triheptanoin in restoring brain energy profiles using ^{31}P phosphorous spectroscopy, and in slowing white matter alterations using diffusion tensor imaging.
- To assess the clinical benefit of triheptanoin on motor function in HD patients using scores on the United Huntington's Disease Rating Scale.
- To assess the clinical benefit of triheptanoin on psychiatric symptoms and cognitive function in HD patients using scores on the PBA-S, SDMT, TMT, Digit span test and Stroop test.
- To assess the effect on quality of life (SF-36) of HD patients of therapeutic use of triheptanoin.
- To confirm long-term clinical and biological tolerance of triheptanoin in HD patients.

SAP001V04/TRIHEP3

Last date of modification: 09/01/2019

Biostatistician: [name]/[name]

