3.5 Secondary endpoints

- Change from baseline to 3, 6 and 12 months in index of brain energy restoration (defined as delta of activation-recovery from the Pi/PCr ratio measured by ³¹phosphorous MRS).
- Change from baseline to 12 months in caudate atrophy as measured by cBSI.
- Change from baseline to 6 and 12 months in DTI metrics and fiber integrity as measured by FBA.
- Change from baseline to 6 and 12 months in TMS and TFC.
- Change from baseline to 6 and 12 months in PBA-s, SDMT, TMT, Digit-Span, Stroop and SF-36.

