4.1 Study design

TRIHEP3 is a phase 2a, multicenter, double-blind, randomized, controlled two-armed study evaluating the efficacy of 1g/kg of body weight triheptanoin per day versus a placebo for a six-month treatment period, followed by a 6-month open-labelled period with all patients treated with triheptanoin.

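### Does testing the Pi/PCr index at M12 alongside M3 and M6 mislead, when both arms are on triheptanoin by M12?

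*SAP*

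**What the plan says.** Section 3.5 lists as one secondary endpoint "Change from baseline to 3, 6 and 12 months in index of brain energy restoration". Section 9 (Secondary criteria) then compares the arms, "The difference between the two groups regarding change from baseline in index of brain energy restoration at M3, M6 and M12", by ANCOVA with the baseline value as covariate, plus a version adjusted for age, gender and BMI. The related objective in Section 3.3 is "To assess the efficacy of triheptanoin in restoring brain energy profiles". The Introduction describes the trial as one "to evaluate the benefit of triheptanoin in early affected HD patients compared to placebo".

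Section 4.1 describes six months of triheptanoin against placebo, "followed by a 6-month open-labelled period with all patients treated with triheptanoin". Section 6.3 keeps patients in their randomised group for analysis. Section 9 describes the study as mainly exploratory and leaves the secondary tests unadjusted for multiplicity. The SAP gives the 12-month comparison no interpretation of its own.

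**The concern.** The three visits share one sentence, one model and one efficacy objective, yet the treatment contrast changes between the second and the third. At M3 and M6 one arm takes triheptanoin and the other control oil. At M12 both take triheptanoin, and only the length of exposure differs.

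The Pi/PCr index looks especially exposed to this. Section 3.1 says that "the Pi/PCr changes in HD patients are stable over time, including over a one-month interval", and that in the proof-of-concept study "the correction of the Pi/PCr response during brain activation was particularly notable when compliance to triheptanoin was ensured". The same section reports "an interesting trend of improved motor functions in HD patients after one month of anaplerotic therapy", which suggests that the earlier study ran over about a month. If the index responds that quickly, the control arm could catch up during the open-label phase. A drug that works would then show differences at M3 and M6 and almost none at M12. A reader who takes the three results as the same contrast could see a lost effect where there was none.

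**Working it through.** **1. What each visit compares.** Let n(t) be the natural course of the index and E(t) the effect after t months of drug, assumed additive and dependent only on exposure time. Exposure comes from Section 4.1 and grouping from Section 6.3.

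| Visit | Triheptanoin arm | Control arm | Difference |
|---|---|---|---|
| M3 | n(3) + E(3) | n(3) | E(3) |
| M6 | n(6) + E(6) | n(6) | E(6) |
| M12 | n(12) + E(12) | n(12) + E(6) | E(12) − E(6) |

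The M12 difference is zero if the effect has levelled off by 6 months of drug. It equals the M6 difference only if E(12) = 2 × E(6).

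**2. The plan's own figure.** Section 5 gives 50 per arm, 80% power and one-sided 0.025 for the caudate endpoint. It gives no mean or SD, so the sample size can only be inverted. The normal approximation gives d = (1.960 + 0.842) × √(2/50) = 0.560; the noncentral t gives 0.566. The SAP states no effect, SD or power for the Pi/PCr index. Using d = 0.566 for that index at M6 is an assumption made for illustration.

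**3. Power at M12 without a response curve.** Take 50 per arm, two-sided 0.05, equal SD and d = 0.566 at M6. If the effect grows by a fraction g between 6 and 12 months of drug, the M12 standardised difference is g × 0.566.

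| g | Power at M12 |
|---|---|
| 0 | 5.0% |
| 10% | 5.9% |
| 25% | 10.8% |
| 50% | 28.8% |
| 100% | 80.0% |

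**4. Power with a first-order approach to a plateau P.** Let E(t) = P[1 − (1 − f)^t], where f is the share of the plateau reached in month 1. Then M12/M6 = (1 − f)^6 and M3/M6 = [1 − (1 − f)^3] / [1 − (1 − f)^6]. For f = 0.10, M12/M6 = 0.9^6 = 0.531 and M3/M6 = 0.271/0.469 = 0.578.

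| f | M12/M6 | M12 power | M3/M6 | M3 power |
|---|---|---|---|---|
| 2% | 0.886 | 70% | 0.515 | 30% |
| 5% | 0.735 | 54% | 0.538 | 33% |
| 10% | 0.531 | 32% | 0.578 | 37% |
| 20% | 0.262 | 11% | 0.661 | 46% |
| 30% | 0.118 | 6% | 0.745 | 55% |
| 50% | 0.016 | 5% | 0.889 | 70% |

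The answer depends almost wholly on f. At f = 5% or less M12 is better powered than M3; from 10% upwards it is worse. The SAP does not say which case applies. In Section 3.1 the stability remark concerns the Pi/PCr changes in HD patients, not how fast the drug acts. The one-month timing belongs to the motor finding, which the SAP itself says may reflect a placebo effect in an open-label study.

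**5. Is anything in the text wrong?** The sentence in Section 9 promises a between-group difference at each of three visits. It specifies no pooling, no common treatment effect and no joint test. The comparison with placebo is stated for the trial as a whole in the Introduction; neither the brain-energy objective nor the M12 analysis is described that way. Read with Sections 4.1 and 6.3, the sentence describes the M12 comparison correctly.

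**6. Can M12 inform efficacy at all?** If the drug does nothing, E(12) = E(6) = 0 and the expected M12 difference is zero. Under the model in step 1, a true difference at M12 therefore implies a drug effect. The inference runs one way only: a difference counts in favour, while a null says little.

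**The case for a change.** The strongest case for a change is that Section 9 is where a contrast should be defined, and that two or three sentences would prevent a foreseeable misreading at almost no cost. The label of exploratory does not answer this, because that sentence of the SAP deals with multiplicity and not with what M12 estimates. The index was also a co-primary endpoint in the earlier protocol described in Section 10, so readers may give it weight. The only objective in Section 3.3 expressed as long-term concerns tolerance, so the M12 efficacy result has no more natural home.

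Much of this stands. M12 is not a controlled comparison, and the SAP does not say so in Section 9. What does not stand is that M12 cannot serve the efficacy objective: it can support a drug effect, though it cannot estimate the effect against control oil. Nor is the point special to the Pi/PCr index or to fast-acting outcomes. It applies equally to 12-month cBSI, the DTI and fibre metrics, the clinical scores and SF-36, because the change in contrast does not depend on speed of response. It is a general feature of a randomised phase followed by an open-label phase, and Section 4.1 states that feature openly.

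**Conclusion.** No change is needed. At M12 the plan compares 12 with 6 months of triheptanoin, and an analyst who follows the SAP as written obtains a valid between-group estimate of that difference. M3 and M6 remain the controlled contrasts, and the month-6 caudate primary is untouched. No rule in the SAP reads a null at M12 as absence of effect. Labelling the 12-month comparisons as early versus delayed start would be a courtesy to readers that can equally be given when results are reported. It would change no data, model, estimate or decision.

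The exposure argument rests on the SAP's own text and is firm. The power figures are not: the 5% to 80% range assumes 80% power at M6, equal SDs, 50 per arm and an additive effect that depends only on exposure. The finer values in step 4 also assume a first-order response. They show how little a null at M12 might mean, not how the trial will behave.
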